### 3.4.4.1 Primary Efficacy Endpoint

The primary measure of efficacy is the overall treatment effect across Week 4, Week 8, Week 12, and Week 16 for change from baseline in exercise capacity, as measured by the 6MWD, for bardoxolone methyl compared to placebo. The difference in mean overall change from baseline through Week 16 (active – placebo) will be used to assess the effect of bardoxolone methyl on 6MWD in patients with PAH. A lower 6MWD reflects greater PAH severity thus, a positive change from baseline suggests an improvement.

As supportive analysis to the primary endpoint, the mean change from baseline and treatment differences will be estimated for each visit. The actual values and changes from baseline in 6MWD will be summarized using descriptive statistics at each scheduled visit. Walk distances collected at any duration other than 6 minutes will not be included in the analysis of 6MWD unless the reason for not walking 6 minutes is one listed in the ATS guidelines as a reason for stopping the test immediately (i.e., chest pain, intolerable dyspnea, leg cramps, staggering, diaphoresis, and pale or ashen appearance).

Baseline for 6MWD will be the average of scheduled predose assessments (e.g., Screen A and Day 1) collected prior to the first administration of study drug. Similarly, two 6MWD measurements collected at Week 4 and again at Week 16. Multiple measures are within the Week 4 and Week 16 visits, and the 6MWD value used as at these visits is the calculated average within these visits.

The mean overall treatment effect across all visits for change from baseline in 6MWD will be estimated and compared with placebo through 16 weeks of treatment by mixed-model repeated measures (MMRM), with treatment group, visit, and the interaction between treatment and visit as fixed factors. Visits at Weeks 4, 8, 12, and 16 will be used. A compound symmetry covariance matrix will be assumed. Point estimates and 95% confidence intervals for the mean change from baseline for each treatment as well as the treatment difference (active-placebo) will be provided overall and at each protocol scheduled timepoint.

Separate mixed models will be used to compare (1) pooled bardoxolone methyl doses with placebo and (2) individual dose levels with placebo. The first model contains two treatment groups with data at four timepoints. Example SAS code to obtain estimated treatment differences is provided below.

```
Proc Mixed data=x order=data;
  Class usubjid trt week;
  model cfb = trt week trt*week /s;
  repeated week / sub = usubjid type = cs;
  Lsmeans trt / diff cl;
  Lsmeans trt*week / diff cl;
Run;
```

SAS ODS output datasets (DIFFS and LSMEANS) can be used to obtain estimated treatment differences overall and at each week.

If the Pearson correlation between baseline BMI and Week 16 change from baseline 6MWD is significant, then baseline BMI will be included as a covariate. Baseline BMI is defined as the last non-missing observation prior to initial dose. Baseline BMI should only be used as a covariate if

the p-value between Week 16 change from baseline 6MWD and baseline BMI is <0.05. Example SAS code to obtain correlation coefficients and p-values is provided below:

```
proc corr data=x pearson;
  where visit='Week 16';
  var bmi cfb;
  ods output PearsonCorr = bmi_corr;
run;
```

Modifications to contrast statements will be required for the model containing individual dose levels. However, ODS output datasets may also be used without modification of SAS code.

[Redacted text block]

[Redacted text block]

[Redacted text block]

[Redacted text block]

[Redacted text block]

[REDACTED]

[REDACTED]

[REDACTED]

[REDACTED]

[REDACTED]

[REDACTED]

[REDACTED]

[REDACTED]

[REDACTED]

[REDACTED]

[REDACTED]

[REDACTED]

[REDACTED]

[REDACTED]

[REDACTED]

- [REDACTED]
- [REDACTED]
- [REDACTED]

[REDACTED]

[REDACTED]

[REDACTED]

[REDACTED]

[REDACTED]

[REDACTED]

[REDACTED]

[REDACTED]

[REDACTED]

[REDACTED]

[REDACTED]

[REDACTED]

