7. INVESTIGATIONAL PLAN

7.1. Overall Study Design

This study consists of two parts: a 16-week double-blind, randomized, placebo-controlled treatment period (“Part 1”), followed by an extension period (“Part 2”). All patients who complete treatment in Part 1 may continue to Part 2. Within Part 1, the study consists of a dose-ranging phase and a dose-titration phase. Qualifying patients with PH in both the dose-ranging and dose-titration phases will be followed for safety, tolerability, and efficacy, and all patients enrolled in the study will follow a similar schedule of assessments.

Part 1

Cohorts 1 and 2: In the dose-ranging phase of Part 1 of the study, up to two independently randomized cohorts may be opened at each dose level and patients will be allocated based on their baseline 6MWD (i.e., Cohort 1 for $6MWD \leq 450$ m and Cohort 2 for $6MWD > 450$ m). Once opened for enrollment, each dose group will include the next eight eligible patients randomized using a 3:1 assignment ratio (bardoxolone methyl:placebo) to be administered once daily for 16 weeks. Within each cohort type, patients will be enrolled to one dose group at a time.

A Protocol Safety Review Committee (PSRC) will assess the starting dose of 2.5 mg and each new dose level of bardoxolone methyl for safety and tolerability based on review of all available data for this study at the time of each review. PSRC reviews will occur after the Week 4 data are available for the first eight patients enrolled at each new dose level combined across both Cohorts 1 and 2. The PSRC assessment will include a dose level recommendation for subsequent dose groups to escalate to a higher dose, proceed to a lower dose, or maintain the current dose. The PSRC may also recommend stopping dosing for current cohorts. Upon completion of dose ranging, the PSRC will continue to meet at regular intervals (approximately quarterly) to monitor safety of all enrolled patients.

Data from all patients enrolled in Cohort 1 (≤ 450 m patients) and Cohort 2 (> 450 m patients) will be used to provide information regarding the optimal dose range for evaluation of safety, tolerability, and efficacy, allowing the sponsor to select an appropriate dose of bardoxolone methyl for further evaluation in patients with WHO Group I PAH. Selecting from PSRC-recommended dose levels, the sponsor will determine the dose level for each subsequent dose group.

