7.3. Treatment Assignment

Patients in Cohorts 1 and 2 will be allocated based on their baseline 6MWD (i.e., Cohort 1 for $6MWD \leq 450$ m and Cohort 2 for $6MWD > 450$ m). Baseline 6MWD for the purpose of cohort determination is calculated as the average of 2 assessments collected prior to randomization. Patients will be randomized to treatment within each dose group in Part 1 of the study using a 3:1 assignment ratio to receive bardoxolone methyl or matching placebo in Cohorts 1 and 2. Patients in Cohorts 1 and 2 will continue their randomized treatment throughout Part 1 and 2 (i.e., no intra-patient dose escalation). However, upon qualifying for the extension period (Part 2), patients randomized to placebo during the treatment period will begin receiving bardoxolone methyl at their group-specific dose. If the Sponsor decides to continue study Part 2 beyond

12 weeks after the last patient enters the extension part of the study all patients may be assigned or re-randomized to the dose(s) selected for further development.

Cohort 3 and Cohort 4 will employ a dose titration scheme intended to identify an optimal dose for each patient. Cohort 3 includes additional WHO Group I patients, while Cohort 4 (PH-ILD cohort) allows only qualified WHO Group III or WHO Group V patients. Cohort 3 will consist of two subcohorts randomized independently within each subcohort using a 2:1 assignment ratio (bardoxolone methyl:placebo) to be administered once daily for 16 weeks. Cohort 4 will consist of four subcohorts randomized independently within each subcohort using a 2:1 assignment ratio (bardoxolone methyl:placebo) to be administered once daily for 16 weeks.

Patients in Cohorts 3 and 4 will start at 5 mg (or placebo) and will dose escalate to 10 mg at Week 4 unless a dose-limiting toxicity (DLT) is reported (Section 7.3.1). If at any time the patient reports an AE that the Investigator considers to be a DLT, the Investigator may choose to decrease the patient's dose to one-half of the prior dose (e.g., 10 mg to 5 mg). The minimum allowed dose is 2.5 mg. Dose escalation during Part 1 is permitted for all patients at Week 4 only.

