##### 3.1.2 Intent-to-treat (ITT) Population

The ITT population includes all randomized patients. The ITT analysis will be done by randomized treatment, pooling all placebo patients within each cohort. No data will be imputed for ITT analyses. The ITT population will be used for analyses of exploratory endpoints except 6MWD. The ITT analysis will be summarized by randomized treatment, pooling all placebo patients and all active patients into various subgroups:

- All PAH patients (Cohorts 1, 2, 3a, and 3b patients)
- All CTD-PAH patients (CTD-PAH patients in Cohorts 1, 2, and 3a)
- All Non-CTD PAH patients (Non-CTD PAH patients in Cohorts 1, 2, and 3b)
- All PH patients (Cohorts 4a, 4b, 4c, 4d)

In addition to the subgroups listed above, the eGFR and pulmonary function testing results will be summarized by individual cohort.

All 6MWD analyses will use the mITT population.

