##### 3.1.3 Modified Intent-to-treat (mITT) Population

The purpose of this Phase 2 study is to estimate the treatment effect of bardoxolone methyl on 6MWD in patients with PAH, and to identify an appropriate dose for further development. Estimated treatment effect from this study will be used to power future trials of bardoxolone methyl in PAH patients.

The mITT population will include all randomized patients who received at least 28 doses of study treatment, did not undergo heart or lung transplantation during the treatment period, and performed at least one post-baseline 6MWT assessment. The primary population for efficacy analyses of the primary endpoint will be the mITT population. The mITT analysis will be done by randomized treatment, pooling all placebo patients and all active treatment patients.

Since treatment effect is expected to be observed within the first few weeks of treatment and sustained over time, missing data will be imputed using last observation carried forward (LOCF) for mITT analyses. Missing data will only be imputed for the 6MWD analysis.

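### In Cohorts 1 and 2 the 6MWD models have no dose-group or enrolment-period term, so individual-dose contrasts rest largely on non-concurrent placebo and would absorb any drift over enrolment

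*SAP*

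**What the plan says.** **Enrolment and randomisation.** Protocol 7.1 says of Cohorts 1 and 2: "Within each cohort type, patients will be enrolled to one dose group at a time". Protocol 7.3 adds: "Patients will be randomized to treatment within each dose group in Part 1 of the study using a 3:1 assignment ratio". Each group has 8 patients. A safety committee reviews each new dose level once Week 4 data are in for its first eight patients, and the sponsor then sets the dose for the next group.

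**Model.** SAP 3.4.4.1 fits change in 6MWD "with treatment group, visit, and the interaction between treatment and visit as fixed factors"; the sample code is "model cfb = trt week trt*week /s". It then plans two versions: "Separate mixed models will be used to compare (1) pooled bardoxolone methyl doses with placebo and (2) individual dose levels with placebo". For the second it says only: "Modifications to contrast statements will be required for the model containing individual dose levels". The one possible covariate is baseline BMI, and only if it correlates significantly with Week 16 change.

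**Placebo set.** SAP 3.4.4.1 does not say which placebo patients enter the individual-dose model. SAP 3.1.2 says of the ITT population: "The ITT analysis will be done by randomized treatment, pooling all placebo patients within each cohort". SAP 3.1.3, on the mITT population used for all 6MWD analyses, says: "The mITT analysis will be done by randomized treatment, pooling all placebo patients and all active treatment patients". SAP section 3 presents analyses by cohort and plans no combination of the same dose across cohorts.

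**The concern.** Because groups open in sequence, dose is tied to calendar time. Only the two placebo patients in a dose group were randomised against that dose. A model with one placebo arm per cohort and no term for group or period compares each dose with placebo patients mostly enrolled earlier or later. The contrast estimates a dose effect only if case mix, background therapy, sites and walk-test conduct did not shift 6MWD change between groups.

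If they did shift it, doses given early or late would look better or worse than placebo with no drug effect at all. The study's primary objective is a dose range, and this is the visible prespecified 6MWD comparison by dose. The pooled-dose model has a milder problem: between-group variation is left in its error term.

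**Working it through.** **1. The plan's own figures.** 8 × 3/4 = 6 active and 2 placebo per group. 38 + 16 + 6 × 24 = 198 and 38 + 16 + 6 × 72 = 486, as Protocol 7.2 states. No SD, effect size or power for the individual-dose comparison is visible.

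**2. Number of groups.** Cohort 2: 16/8 = 2. Cohort 1: 38/8 = 4.75, so the count cannot be derived. The protocol synopsis lists four doses, so four groups is the main case and five a variant.

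**3. Share of non-concurrent placebo (pooled within cohort).** Four groups: 6 of 8. Five groups: 8 of 10. Cohort 2: 2 of 4.

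**4. Bias.** Let 6MWD change drift by δ per successive group. Pooled placebo sits at the average period, so the first and last doses are biased by (G − 1)/2 × δ in opposite directions: 1.5δ with four groups, 2δ with five.

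**5. How often the 95% CI excludes zero with no drug effect.** With all four visits filled by LOCF and compound symmetry, the overall contrast equals a linear model on patient means, so that was simulated (two-sided 5%; drift in units of the between-patient SD of mean change).

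| Drift per group | End dose, 4 groups | End dose, 5 groups |
|---|---|---|
| 0 | 5% | 5% |
| 0.1 SD | about 6% | about 7% |
| 0.2 SD | about 8–9% | about 11–12% |
| 0.3 SD | about 12–13% | about 19–20% |

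The ranges span separate simulation runs of different size. With four groups the middle doses stay at about 5–6%. In metres, again assumed: at SD 40 m, the end-dose figure is 10.0% for 10 m drift per group and 24.4% for 20 m. At 5 m per group it is at most about 7% for any SD from 30 to 60 m. In Cohort 2 (two groups, SD 40 m) it is 5.3% at 10 m and 6.4% at 20 m.

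**6. Pooled-dose model.** Every group contributes the same 3:1 mix, so drift cancels from the difference. It stays in the residual variance, which becomes 1 + 8Σ(g − ḡ)²δ²/(8G − 2). Four groups, δ = 0.3 SD: 1 + 8 × 5 × 0.09/30 = 1.12, so the interval is √1.12 = 1.06 times as wide as it need be. Its CI excluded zero in 1.4–5.1% of runs over all settings tried: conservative, not inflated.

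**7. Price of an enrolment-order covariate in the individual-dose model.**

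- Dose versus placebo: SE² = 1/6 + 1/(2G) + (g − ḡ)²/[2Σ(g − ḡ)²].
  - Four groups, end dose: √(1/6 + 1/8 + 2.25/10) = 0.719 SD, against √(1/6 + 1/8) = 0.540 without it: +33%.
  - Five groups, end dose: √(1/6 + 1/10 + 4/20) = 0.683 against 0.516: +32%.
- First versus last dose: SE² = 1/6 + 1/6 + (G − 1)²/[2Σ(g − ḡ)²].
  - Without the covariate: √(1/3) = 0.577.
  - Five groups: √(1/3 + 16/20) = 1.065, +84%.
  - Four groups: √(1/3 + 9/10) = 1.111, +92%.
  - Cohort 2: √(1/3 + 1) = 1.155, twice as wide.
- Concurrent placebo only (6 versus 2): √(1/6 + 1/2) = 0.816 SD, or 1.51 times the four-group pooled SE.

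**The case against.** Several points on the other side stand.

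- **No decision rule.** The plan gives estimates and 95% CIs, states no alpha, calls the study exploratory (SAP 1.9) and lets no single endpoint settle the dose range (SAP 1.5.2). A reader might infer that a formal test will falsely declare a dose effective. The documents set no such test; the percentages above describe intervals.
- **6MWD is one input among many.** Dose escalation rests on fluid overload, safety laboratory data, vital signs and pharmacodynamic markers (Protocol 9.6.3). The larger titration cohorts, which the SAP's rationale makes the focus of efficacy, do not examine dose levels.
- **The placebo set is inferred.** The ITT wording is not for 6MWD, and the mITT wording also pools all active patients, so it cannot fully describe an individual-dose model. Pooling within cohort is likely, not stated.
- **Dose and order need not match.** The committee may recommend holding or lowering the dose, so a dose could span several groups, which would weaken the confounding. Five distinct doses cannot be derived from the documents.
- **Drift is hypothetical.** The endpoint is already a change from baseline, background therapy must be stable at entry, and the walk test is scripted.
- **Unseen text.** Redacted blocks follow the model code, and ad hoc sensitivity analyses are allowed (SAP 3.4.4).

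None of this removes the structural gap. The visible SAP neither adjusts for enrolment period nor warns that the dose contrasts are partly non-randomised, and an ad hoc check is not a planned one.

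**Conclusion.** The concern holds as a conditional weakness. On the natural reading of the pooling, individual-dose 6MWD contrasts in Cohort 1 are mostly non-concurrent, and drift would bias the first and last doses. With four sequential doses the end-dose interval would wrongly exclude zero about 8–9% of the time at 0.2 SD drift per group and about 12–13% at 0.3 SD, against 5%. Five groups would give about 11–12% and 19–20%. All of this assumes linear drift and distinct doses in sequence; nothing in the documents shows that drift occurred or how large it was.

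The effect is small in Cohort 2 and absent in Cohorts 3 and 4. A reader might infer that the pooled-dose result is biased too. Within Cohort 1 or 2 it essentially is not, because each group has the same allocation (mITT exclusions could disturb this slightly); its interval is merely too wide under drift.

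A reader might also conclude that a difference between doses should count only if it survives adjustment for enrolment order. That does not follow: the adjustment raises the first-versus-last SE by 84% with five groups and more with fewer, so such a rule could hardly be met, and it would conflict with the SAP's choice of judgement on the totality of data.

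**What to change.** In SAP 3.4.4.1, for Cohorts 1 and 2:

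1. **Pooled-dose model.** Add dose group, the unit of randomisation, as a fixed factor. Cost: 3 degrees of freedom in Cohort 1 with four groups (4 with five), and 1 in Cohort 2.
2. **Individual-dose model.** State that placebo is pooled within cohort and label the contrasts as partly non-randomised. Beside them, as a sensitivity analysis only, report the same model with enrolment order or randomisation date as a covariate. Cost: dose-versus-placebo SE about a third wider for the end doses, and the first-versus-last SE nearly doubled. The correction is exact only for linear drift. It is an aid to reading the dose contrasts, not a condition for believing them.
3. **Display.** Tabulate placebo 6MWD change by dose group so that drift can be seen, bearing in mind that each row has about two patients.

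All three use data already collected and need only SAP wording, one added term, one extra model run and one table.

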#### 1.8 Study Cohorts

As described in Section 1, this study includes 2 cohorts in the dose-ranging phase and 6 sub-cohorts (within 2 overarching cohorts) in the dose-titration phase. Analyses described in this SAP may be performed separately by cohort. The Part 1 and Part 2 safety and efficacy analyses will be summarized by randomized treatment, pooling all placebo patients and all active patients into various subgroups:

- All PAH patients (Cohorts 1, 2, 3a, and 3b patients)
- All CTD-PAH patients (CTD-PAH patients in Cohorts 1, 2, and 3a)

- All Non-CTD PAH patients (Non-CTD PAH patients in Cohorts 1, 2, and 3b)
- All PH patients (Cohorts 4a, 4b, 4c, 4d)

In addition to the subgroups listed above, the eGFR, six-minute walk test, and pulmonary function testing results will be summarized by individual cohort.

All patients enrolled in the study will follow the same schedule of assessments, including a placebo-controlled period (Part 1) followed by an extension period (Part 2).

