### 3.3 Analysis of Treatment Group Comparability

Demographic information (age, sex, ethnicity, race), baseline characteristics (baseline BMI, weight) and baseline disease characteristics (including PAH classification and details, time since diagnosis, baseline PAH concomitant medications, thromboembolic disease assessment, pulmonary function testing, oxygen use during 6MWTs and available baseline right heart catheterization data) will be summarized by treatment arm for all randomized patients.

Descriptive baseline summaries of continuous data will present the group mean, standard deviation, median, minima, and maxima. Descriptive summaries of discrete data will present the category counts as frequencies and percentages.

Unless otherwise stated, the baseline value of any variable will be defined as the last available value recorded prior to the first administration of bardoxolone methyl/placebo. Missing values will not be imputed, unless otherwise noted, and will be tabulated as missing.

### 3.4 Analysis of Part 1

Part 1 data will be analyzed using the analysis populations defined in [Section 3.1](#). Separate analyses will be performed by each cohort. Part 1 analyses will only include data from the placebo controlled portion of the study. If a subject does not complete Part 1, or chooses not to enter Part 2, then all their data will be used in Part 1. If a subject enters Part 2, then all data up to and including the Week 16 visit will be included in Part 1.

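### The visible primary 6MWD model leaves out baseline 6MWD and, where PAH cohorts are pooled, the cohort within which patients were randomised

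*SAP*

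**What the plan says.** SAP 3.4.4.1 describes a repeated-measures model for change from baseline in 6MWD at Weeks 4, 8, 12 and 16, "with treatment group, visit, and the interaction between treatment and visit as fixed factors". The example code agrees: "model cfb = trt week trt*week /s". Its class statement lists patient, treatment and week, but not cohort.

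The same section defines the baseline ("Baseline for 6MWD will be the average of scheduled predose assessments"), but in the visible text it serves only to form the change score. The one covariate mentioned is baseline BMI, which enters only if its correlation with Week 16 change has p < 0.05.

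On which patients are analysed together, the SAP says two things:

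- **Pooled.** SAP 1.8 plans Part 1 efficacy by randomised treatment, "pooling all placebo patients and all active patients into various subgroups"; one group is All PAH (Cohorts 1, 2, 3a, 3b). SAP 3.1.3 says: "The mITT analysis will be done by randomized treatment, pooling all placebo patients and all active treatment patients". The Rationale for Version 3.0 lists a pooling strategy for the primary analysis among its changes.
- **By cohort.** SAP 3.4: "Separate analyses will be performed by each cohort". SAP 1.9.3 times the primary Part 1 analysis cohort by cohort, SAP 3 presents all analyses by cohort, and SAP 3.4.4 pools active doses within cohort. SAP 1.8 itself adds: "In addition to the subgroups listed above, the eGFR, six-minute walk test, and pulmonary function testing results will be summarized by individual cohort".

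Protocol 7.1, 7.3 and 9.5 randomise within cohort or subcohort: 3:1 in Cohorts 1 and 2 (by dose group), 2:1 in each subcohort of Cohorts 3 and 4.

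**The concern.** SAP 3.1.3 states the use of the result: "Estimated treatment effect from this study will be used to power future trials of bardoxolone methyl in PAH patients". SAP 1.10 explains that the endpoint was changed to get more information from each patient on a highly variable measure. Leaving out the baseline of that same measure works against this aim.

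In a pool that mixes 3:1 and 2:1 cohorts, treatment and cohort are partly confounded. If mean change differs between the dose-ranging and titration phases, part of that difference is counted as treatment effect. A reader who plans a later trial also needs to know whether the pooled or the by-cohort estimate is the primary one.

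**Working it through.** **Stated figures.** Protocol 7.2 gives 38 + 16 + 6 × 24 = 198 planned and 38 + 16 + 6 × 72 = 486 at maximum. Both reproduce. The visible text gives no SD, correlation, effect size or power for 6MWD, so those values below are assumptions.

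**Baseline adjustment.** Part 1 6MWD is completed by LOCF, so the overall contrast is essentially a difference in four-visit means. Set all variances to 1 with common correlation r between any two walks:

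- change-score variance: (1+3r)/4 + 1 − 2r = 5(1−r)/4
- residual variance after adjusting for baseline: (1+3r)/4 − r² = (1−r)(1+4r)/4
- ratio: (1+4r)/5 = 0.76, 0.84, 0.92 at r = 0.7, 0.8, 0.9
- cost of estimating the slope: a factor of about 1 + 1/(n−4)

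| Group | Slope cost | Net saving at r = 0.7 / 0.8 / 0.9 |
|---|---|---|
| All PAH, n = 102 | 1.010 | 23% / 15% / 7% |
| One subcohort, n = 24 | 1.050 | 20% / 12% / 3% |

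Cohorts 1 and 2 are cut at a baseline of 450 m, which shrinks baseline variance and leaves the regression slope unchanged. If a fraction t of the variance is retained, the ratio becomes (1+4r)/(1+4r+4t(1−r)).

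| Group | Assumed t | Slope cost | Net saving at r = 0.7 / 0.8 / 0.9 |
|---|---|---|---|
| Cohort 1, n = 38 | 0.4 to 0.6 | 1.029 | 9–14% / 4–8% / 0.5–2% |
| Cohort 2, n = 16 | 0.25 | 1.083 | 0% / −3% / −6% |

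For example, Cohort 2 at r = 0.9: 4.6/4.7 × 1.083 = 1.06, a 6% loss.

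Unequal variances also matter. Without truncation, if the follow-up SD is 10% below the baseline SD, the gross savings are 37%, 32% and 28%. If it is 10% above, they are 13%, 5% and 0%, and at r = 0.9 the slope cost leaves a net loss of about 1% at n = 102 and 5% at n = 24.

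**Cohort term, All PAH pool.** At exact ratios and planned sizes:

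- Cohorts 1 and 2: 54 patients, 40.5 active and 13.5 placebo
- Cohort 3: 48 patients, 32 active and 16 placebo
- share of active patients from Cohorts 1 and 2: 40.5/72.5 = 55.9%
- share of placebo patients from Cohorts 1 and 2: 13.5/29.5 = 45.8%
- gap: 10.1 points
- at maximum enrolment: 40.5/136.5 − 13.5/61.5 = 7.7 points

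The gap is an expected value, not a bound. Cohort 1 has 38 patients, which is not a multiple of eight. A 28:10 split gives 40/72 − 14/30 = 8.9 points; 29:9 gives 41/73 − 13/29 = 11.3 points. If the mITT rule removed an assumed 10% of active patients in Cohort 3 only, the gap would be 12.7 points; in Cohorts 1 and 2 only, 7.5 points.

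For an assumed between-phase difference of 10 to 30 m in mean change, the shift is 0.101 × 10 = 1.0 m to 0.101 × 30 = 3.0 m. The standard error is SD × √(1/72.5 + 1/29.5) = 0.218 × SD:

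- 10.9 m if the four-visit average has an SD of 50 m
- 9.1 m if 50 m is the single-visit SD with correlation 0.6 (average SD 50 × √0.7 = 41.8 m)

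**Type I error.** A between-cohort difference left out of the model also enters the residual and widens the estimated standard error. In simulations of the unadjusted All PAH comparison at planned sizes (4,000 runs per setting, phase differences of 20 and 40 m), rejection under no effect was 4.2% to 5.0%. With cohort in the model, the bias fell to about zero.

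**Cost of the cohort term if cohorts do not differ.** The sum of (active × placebo)/n over Cohorts 1, 2, 3a and 3b is 7.125 + 3 + 5.333 + 5.333 = 20.79. Its reciprocal, 0.0481, compares with 0.0477 unadjusted, so variance rises by about 0.8%.

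**The case against.** The strongest reply is that the by-cohort passages govern. SAP 1.9.3 ties the primary Part 1 analysis to the cohort, SAP 3.4.4 names the cross-cohort pools only for plots, and no visible sentence says that this model is fitted to the All PAH pool. On that reading, the cohort half of the point falls away. It stands only where the PAH pools are modelled, which SAP 3.1.3 and the Rationale for Version 3.0 suggest. A reader might infer that nothing identifies the primary estimate. That is too strong: several passages point to by-cohort analysis and others to pooling, and they need reconciling.

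Second, a change-score model is valid within a randomised cohort, the study is exploratory (SAP 1.9), no single endpoint decides the dose range (SAP 1.5.2), and ad hoc sensitivity analyses are allowed (SAP 3.4.4). All of this stands, and it limits the consequence. It does not remove the likely precision gain in the pool and the Cohort 3 and 4 subcohorts.

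Third, the correlations, variances and phase difference are assumed, and baseline adjustment can lose a little precision in a small or truncated cohort. This also stands, and the fix allows for it. Finally, the text after the code is redacted, so adjusted supportive analyses cannot be ruled out.

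**Conclusion.** The two omissions are clear in the visible text and code. Leaving out baseline 6MWD probably gives up 7% to 23% of variance in the All PAH pool and 3% to 20% in a 24-patient subcohort, for r from 0.9 down to 0.7 with equal variances. The gain is smaller in Cohort 1 and ranges from nil to a 6% loss in Cohort 2. Leaving out cohort shifts the All PAH estimate by 1 to 3 m for an assumed 10 to 30 m phase difference, well inside a standard error of 9 to 11 m. The CTD and non-CTD PAH pools mix the same ratios, but the documents do not split Cohorts 1 and 2 by CTD status, so their shifts cannot be computed. There is no ratio-driven bias within a single cohort or in the Cohort 4 pool, where every subcohort is 2:1.

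A reader might infer that the pooled test is anti-conservative. Adding the shift to a fixed standard error would suggest so, but with the standard error that the model estimates, type I error stays near 5%. This is an improvement in precision and clarity, not a validity failure.

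**What to change.** - Add baseline 6MWD and its interaction with week to the model for the pooled analyses and the Cohort 3 and 4 subcohorts. Leave it optional in a standalone Cohort 2 model, where it may cost a few percent in variance.
- Add cohort (1, 2, 3a, 3b; or 4a to 4d) as a factor in every model that pools cohorts. All dose groups in Cohorts 1 and 2 use 3:1, so this removes the ratio-driven confounding without a dose-group term.
- Reconcile SAP 1.9.3, 3, 3.4 and 3.4.4 (by cohort) with the Rationale for Version 3.0, 1.8 and 3.1.3 (pooled). State which 6MWD estimate is primary and will be used to power later trials.
- Minor: decide beforehand whether BMI is in the model, rather than by its p-value against the outcome.

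The cost is a few lines of SAP text and code, with no new data. If the terms turn out to be unhelpful, the price in variance is about 0.8% for cohort, and for the baseline slope about 1% at n = 102 and 5% at n = 24.
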